1.2 Schema

Figure 1 Study Design Part 1

[figure not shown]

CCI

SRC = Safety review committee

Participants may also be required to attend a Visit up to approximately 2 years after randomisation for a follow-up ADA sample.

Figure 2 **Study Design Part 2**

CCI

SRC = Safety review committee

1.3 Schedule of Activities

Once informed consent has been obtained, e-Diary provision and training for site and home visits should occur first during Visit 1, followed by PRO assessments. The PRO assessments should be conducted first at all other visits. For all participants, in-clinic spirometry testing must be initiated between 6:00 AM and 11:00 AM during the Screening, Rescreening, and Run-in Period.

Whenever ECGs, vital signs, and blood draws are scheduled for the same nominal time, the order should be as follows: ECGs, vital signs (vital signs can occur immediately after ECG using the same rest period), then blood draws. The timing of the first 2 assessments should be such that it allows the blood draw (eg, PK blood sample) to occur at the assigned nominal time.

FeNO and spirometry should follow above assessments. Whenever FeNO and spirometry are scheduled for the same nominal time, the order should be as follows: FeNO followed by spirometry.

Nasal/nasopharyngeal/oropharyngeal sampling should be performed last.

Safety urine samples may be collected at any time during the visit.

If required, the order of assessments may be modified in consultation with the Sponsor Study Physician.

Refer to Section 8 for details on the study assessments.

Table 1 Schedule of Activities Part 1

Procedure	Screening	Run-in	Treatment Period ^a								ETV/ IPD	Follow-up		Details in CSP Section or Appendix	
			3			4,5,6	7		8	9					
Visit	1	2	3			4,5,6	7		8	9		10	11		
Day	(up to 14 days before V2) ^{b,c}	-28 ± 2	-1	1	2 to 13	14	16, 20, 24	28 ^d - 2	29	30	32		39 ± 6	56 ± 4	
Signed informed consent	X														5.1
Admission			X					X							4.1.1
Discharge						X ^e			X						4.1.1
Optional residential stay (throughout Treatment Period)							X								4.1.1
Inclusion and exclusion criteria	X	X	X	X											5.1, 5.2
Demography	X														5.1
Medical/surgical history	X														5.1
Smoking history including cotinine testing	X							X							5.1
Asthma history	X														5.1
Concomitant medication	X	X	X	X	X	X	X	X	X	X	X	X	X	X	6.5
Height/weight ^f	X							X						X	8.2.1
Physical examination	X ^g			X ^h					X ^h			X ^g	X ^h	X ^g	8.2.1
Vital signs (blood pressure, pulse rate, temperature, respiratory rate) ⁱ	X	X	X	X	X	X	X	X	X	X	X	X	X	X	8.2.2
Study drug inhalation training		X	X	X ^j											6.1.3
Home device dispensation (FeNO and spirometer)		X													6.1.2
Home device training (FeNO and spirometer)		X		X ^j											6.1.2

Table 1 Schedule of Activities Part 1

Procedure	Screening	Run-in	Treatment Period ^a								ETV/ IPD	Follow-up		Details in CSP Section or Appendix	
			3			4,5,6	7		8	9					
Visit	1	2	3			4,5,6	7		8	9		10	11		
Day	(up to 14 days before V2) ^{b,c}	-28 ± 2	-1	1	2 to 13	14	16, 20, 24	28 ^d - 2	29	30	32		39 ± 6	56 ± 4	
Rescue medication (eg, salbutamol) ^k	X	X	X	X	X	X	X	X	X	X	X	X	X	X	6.5.1
FeNO test (in-clinic) ^l	X	X	X	X	X	X	X	X	X	X	X	X	X	X	8.1.3
FeNO at-home assessments (Niox Vero) ^{l, m}		X				X	X			X	X	X	X	X	8.1.3
Spirometry (FEV ₁ and FVC) ⁿ	X	X	X	X	X	X	X	X	X	X	X	X	X	X	8.1.1
12-lead ECG ^o	X			X	X (Day 7)	X		X							8.2.3
ACQ-6	X	X		X	X (Day 7)	X	X (Day 20)	X			X				8.1.10
FEV ₁ /PEF (home device) ^p		X	X	X	X	X	X	X	X	X	X	X	X	X	8.1.1, 8.1.11
Cough VAS		X	X	X	X	X	X	X	X	X	X	X	X	X	8.1.10
SPFQ (optional)		X				X					X		X	X	8.1.10
Assign e-Diary ^q	X														8.1.4
Dispense e-Diary ^r		X													8.1.4

Table 1 Schedule of Activities Part 1

Procedure	Screening	Run-in	Treatment Period ^a								ETV/ IPD	Follow-up		Details in CSP Section or Appendix	
Visit	1	2	3				4,5,6	7		8	9		10	11	
Day	(up to 14 days before V2) ^{b,c}	-28 ± 2	-1	1	2 to 13	14	16, 20, 24	28 ^d - 2	29	30	32		39 ± 6	56 ± 4	
Check e-Diary compliance			X	X	X	X	X	X	X	X	X	X	X	X	6.4.2
Check compliance with background medication			X	X	X	X	X	X	X	X	X	X	X	X	6.5
Collect e-Diary												X		X	8.1.4
Asthma symptom score and rescue medication use		X	X	X	X	X	X	X	X	X	X	X	X	X	8.1.6, 8.1.7
Study drug dispensation						X									6.1
Study drug administration ^s	CCI														6.1.3
Drug accountability								X				X			6.2
Return unused medication and DPI								X				X			6.2
AEs ^t	X	X	X	X	X	X	X	X	X	X	X	X	X	X	8.3
Blood samples for biochemistry	X	X		X ^u	X ^v	X	X	X		X		X	X	X	8.2.4
Blood samples for haematology	X	X		X ^u	X ^v	X	X	X		X		X	X	X	8.2.4
Blood samples for clotting profile	X	X		X ^u	X ^v	X	X	X		X		X	X	X	8.2.4
Blood samples for CRP (local laboratory) ^w			X	X	X	X	X	X	X	X	X	X	X	X	8.2.4
Blood sample for hs-CRP	X	X		X ^u	X ^v	X	X	X		X		X	X	X	8.2.5.1
Blood samples for safety immuno-biomarkers	X	X		X ^u	X ^v	X	X	X		X		X	X	X	8.2.4
Blood samples allergen-specific IgE ^x			X												8.6.1

Table 1 Schedule of Activities Part 1

Procedure	Screening	Run-in	Treatment Period ^a								ETV/ IPD	Follow-up		Details in CSP Section or Appendix	
			1	2	3			4,5,6	7		8	9			
Visit	1	2	-1	1	2 to 13	14	16, 20, 24	28 ^d - 2	29	30	32	10	11		
Day	(up to 14 days before V2) ^{b,c}	-28 ± 2											39 ± 6	56 ± 4	
Blood samples for serum pregnancy test (all female participants)	X														5.1, 8.2.4
Blood samples for Hepatitis B (HBsAg, anti-HBs, anti-HBc), and C; HIV-1 and HIV-2; QFT for TB ^y	X														5.1, 8.2.4
Blood samples for PK measurements ^z				X	X	X	X	X	X	X	X	X	X	X	8.5.1
Blood samples for ADA ^{aa}				X		X	X (Day 20, 24)	X				X	X	X	8.5.2
CCI [REDACTED] bb				X											8.6.2, 8.7
CCI [REDACTED]				X (pre-dose)				X (pre-dose)				X	X	X	8.6.2
Urinalysis	X	X		X ^u	X ^v	X	X	X	X	X	X	X	X	X	8.2.4
Blood samples for FSH (if needed to confirm postmenopausal status in female participants < 50 years and not on HRT)	X														5.1, 8.2.4

Table 1 Schedule of Activities Part 1

Procedure	Screening	Run-in	Treatment Period ^a								ETV/ IPD	Follow-up		Details in CSP Section or Appendix		
			1	2	3			4,5,6	7		8	9				
Visit	1	2	-28 ± 2	-1	1	2 to 13	14	16, 20, 24	28 ^d - 2	29	30	32		10	11	
Day	(up to 14 days before V2) ^{b,c}													39 ± 6	56 ± 4	
Urine pregnancy test (females of childbearing potential) ^{cc}			X						X					X	X	5.1, 8.2.4
Urine drug screen	X								X							5.2, 8.2.4
SARS-CoV-2 PCR ^{dd}	X	X	X ^{ee}	X	X	X	X	X	X	X	X	X	X	X	X	5.2, 8.2.4
SARS-CoV-2 serology ^{dd}	X													X	X	5.2, 8.2.4

Abbreviations: ACQ-6 = Asthma Control Questionnaire-6; ADA = anti-drug antibody; AE = adverse event; AESI = adverse event of special interest; **CCI** COVID-19 = Coronavirus disease-2019; CRP = C-reactive protein; CSP = clinical study protocol; DPI = dry powder inhaler; ECG = electrocardiogram; e-Diary = electronic diary; ETV = early termination visit; FEV₁ = forced expiratory volume in 1 second; FeNO = fractional exhaled nitric oxide; FSH = follicle stimulating hormone; FVC = forced vital capacity; **CCI** HBsAg = hepatitis B surface antigen; HIV = human immunodeficiency virus; **CCI** HRT = hormone replacement therapy; hs-CRP = high sensitivity CRP; IgE = immunoglobulin E; IPD = Intervention Discontinuation Visit; **CCI** PCR = polymerase chain reaction; PEF = peak expiratory flow; PK = pharmacokinetics; QFT = QuantiFERON; SARS-CoV-2 = severe acute respiratory syndrome coronavirus 2; SPFQ = Study Participant Feedback Questionnaire; SoA = Schedule of Activities; TB = tuberculosis; VAS = Visual Analogue Scale

^a In-clinic outpatient visits during the Treatment Period will be scheduled so that they fall at the time of morning dose administration.

^b Time between Visit 1 and Visit 2 may be extended up to 28 days upon input from the Study Physician.

^c Visit 1 can be done on several/different days prior to Visit 2.

^d Participants may be admitted on Day 27. Day 28 should be performed on the scheduled calendar day as far as possible; the -2-day window may be utilised only if required. If the -2-day window is utilised, all subsequent visits will be adjusted to follow time window between visits as specified in the SoA.

^e Discharge on Day 14 after the morning post-dose procedures.

^f Height only at Visit 1.

^g A complete physical examination including an assessment of the general appearance, respiratory, cardiovascular, abdomen, skin, head and neck (including ears, eyes, nose and throat), lymph nodes, thyroid, musculoskeletal and neurological systems will be performed.

^h A brief physical examination including an assessment of the general appearance, skin, abdomen, cardiovascular, and respiratory systems will be performed.

ⁱ Vital signs to be performed BID whilst participants are in-clinic. Vital signs will be measured pre-dose at the scheduled morning dose in-clinic visits and additionally prior to the evening dose if participants receive the evening dose at the clinic (eg, due to optional overnight stay).

^j Refresher training as required.

^k Rescue medication to be as necessary. Check if participant has enough rescue medicine for use at-home use and refill if necessary.

^l FeNO will be measured pre-spirometry, pre-dose (as applicable), and pre-bronchodilation.

- m FeNO assessments at home will only be performed (morning and evening) at non-clinic visit timepoints.
- n In-clinic spirometry on Days 1 to 14 and Day 28 will be performed pre-dose and 2 h post-dose (\pm 15 min) in the morning (prior to taking controller medication) and on Days 1 to 13 pre-dose and 4 h post-dose (-2 h) in the evening. Where possible, all post-randomisation morning pre-dose clinic spirometry assessments should be performed within \pm 30 minutes of the time that the randomisation spirometry was performed during the residential period. The evening pre-dose spirometry should also be performed within a \pm 30 minutes window relative to the evening assessment timepoint. If patients remain in the unit without discharge to stay overnight during Days 14 to 27, a pre-dose and 2 h post-dose spirometry assessment will be performed in the morning (prior to taking controller medication) and pre-dose and 4 h (-2h) post-dose spirometry assessment in the evening. If patients are discharged and re-admitted to the unit for overnight stay on Days 15 to 27, the morning and evening post-dose spirometry assessment will be 4 h (-2h) post-dose (controller medication timing will remain unchanged from home dosing and controller medication will be taken directly after study intervention). At clinic visits with no overnight stay, morning pre-bronchodilator and 2 h post spirometry will be performed. The timing of controller medication and clinic post-dose spirometry assessments may be adjusted by the Sponsor.
- o ECG will be measured before (within 75 min) and 1 hour (\pm 10 min) after administration of study intervention on visits as indicated.
- p Home device spirometry will be performed pre-dose twice daily, including on in-clinic assessment days. On in-clinic assessment days, home spirometry may be performed up to 2 hours prior to dosing.
- q At Visit 1 the e-Diary is set up, participants perform training and ACQ-6 and SNOT-22 is completed.
- r The e-Diary will be completed twice daily during the Run-in, Treatment, and Follow-up Period.
- s Study intervention will be administered CCI [REDACTED]
[REDACTED] While at clinic, the study drug administration will be monitored by the site staff. Administration will be registered in the e-Diary by the participant.
- t AEs will be collected from the time of informed consent. Unscheduled safety sampling may be performed at the discretion of the Investigator in the event of AEs/AESIs, including but not limited nasal swabs to confirm infection.
- u Baseline safety sampling will be performed pre-dose on Day 1.
- v Sampling on Days 2, 6, 8, 10, and 12.
- w CRP must be done locally on Day -1 (may be performed on Day -2 for logistical reasons) to confirm eligibility as per inclusion criterion 26. It may be performed throughout the study in the event of AE/AESI as required to inform suspension/stopping criteria.
- x Blood samples will be analysed for IgE if potential drug related IgE response is observed in any participant; may be collected on Day -1 or Day 1 pre-dose.
- y PCR may be performed to confirm hepatitis B / hepatitis C status if required.
- z Blood samples for PK measurements will be collected for all participants. Timing of samples: Day 1 pre-dose (-60 min), 1, 2, 3 (\pm 10 min), 4, 6, 8 (\pm 20 min) and 12 h (up to 1h prior to the next dose, must be before the subsequent dose); Day 28 pre-dose (-60 min), 1, 2, 3 (\pm 10 min), 4, 6, 8 (\pm 20 min), and 12h (\pm 1 h; single dose of AZD1402 only on Day 28). Pre-dose on Days 2, 4, 6, 8, 10, 12, 14, 16, 20, 24 (up to 1 h prior to the next dose, must be before the subsequent dose), 29 (24 h \pm 2 h after Day 28 dose), 30 (48 h \pm 2.5 h after Day 28 dose), 32 (96 h \pm 2.5 h after Day 28 dose), 39 (\pm 6 days), and 56 (\pm 4 days). Part Ib only: Day 20, 4 h post-morning dose (\pm 20 min). The PK sampling timepoints may be amended based on results from Part 1a/b. An unscheduled PK sample may be collected in the case of AEs and / or unscheduled safety blood sampling.
- aa ADA sampling, pre-dose Day 1, Day 14, Day 20, Day 24 (Part 1b only) and Day 28 and on Follow-up/unscheduled visits. CCI [REDACTED]
[REDACTED] An unscheduled ADA sample may also be collected in case of AEs/AESIs and/or unscheduled safety blood sampling.
- bb Sample collection if consented only. If for any reason the sample is not drawn at Visit 3, it may be taken at any visit until the last study visit.
- cc All urine pregnancy tests will be done pre-dose.

dd SARS-CoV-2 serology at Screening, End of Trial and final Follow-up Visits; PCR is optional and may be performed centrally or at the local laboratory as clinically indicated and as per local guidelines for the duration of the study. Ad hoc nasal and/or throat-swab specimen is to be collected for the identification of a suspected respiratory infection during any visit. This may be performed locally, or if required by central laboratory.

ee May be performed on Day -2 for logistical reasons.

Table 2 Schedule of Activities Part 2

Procedure	Screening	Run-in	Treatment Period ^a					ETV/ IPD	Follow-up		Unscheduled Visit	Details in CSP Section or Appendix
Visit	1	2	3	4	5	6	7		8	9		
Day	(up to 14 days before V2) ^{b,c}	-28 ± 2	1	7 ± 2	14 ± 2	21 ± 2	28 ± 2		39 ± 6	56 ± 4		
Week	-6	-4	0	1	2	3	4		5/6	8		
Signed informed consent	X											5.1
Inclusion and exclusion criteria	X	X	X									5.1, 5.2
Demography	X											5.1
Medical/surgical history	X											5.1
Smoking history including cotinine testing	X											5.1
Asthma history	X											5.1
Concomitant medication	X	X	X	X	X	X	X	X	X	X		6.5
Height/weight ^d	X						X					8.2.1
Physical examination	X ^e		X ^f				X ^f	X ^f	X ^f			8.2.1
Vital signs (blood pressure, pulse rate, temperature, respiratory rate) ^g	X	X	X	X	X	X	X	X	X	X		8.2.2
Study drug inhalation training		X	X ^h									6.1.3
Home device (spirometer) dispensation		X										6.1.2
Home device training (spirometer)		X	X ^h									6.1.2
Rescue medication (eg, salbutamol) ⁱ	X	X	X	X	X	X	X	X	X	X		6.5.1
FeNO test (in-clinic) ^j	X	X	X	X	X	X	X	X	X	X	X	8.1.3
Spirometry (FEV ₁ and FVC) ^k	X	X	X	X	X	X	X	X	X	X	X	8.1.1
Reversibility test ^l	X											8.1.2
12-lead ECG ^m	X		X				X	X				8.2.3
ACQ-6	X	X	X	X	X	X	X	X	X	X		8.1.10

Table 2 Schedule of Activities Part 2

Procedure	Screening	Run-in	Treatment Period ^a					ETV/ IPD	Follow-up		Unscheduled Visit	Details in CSP Section or Appendix
Visit	1	2	3	4	5	6	7		8	9		
Day	(up to 14 days before V2) ^{b,c}	-28 ± 2	1	7 ± 2	14 ± 2	21 ± 2	28 ± 2		39 ± 6	56 ± 4		
Week	-6	-4	0	1	2	3	4		5/6	8		
SPFQ (optional)		X		X		X		X		X ⁿ		8.1.10
FEV ₁ /PEF (home device) ^o		X	X	X	X	X	X		X			8.1.1, 8.1.11
Assign e-Diary ^p	X											8.1.4
Dispense e-Diary ^q		X										8.1.4
Check e-Diary compliance			X	X	X	X	X	X	X	X	X	6.4
Check compliance with background medication			X	X	X	X	X	X	X	X	X	8.1.4
Check compliance with study medication			X	X	X	X	X				X	
Collect e-Diary								X		X		8.1.5
Asthma symptom score and rescue use		X	X	X	X	X	X	X	X			8.1.6, 8.1.7
Study drug dispensation			X		X							6.1
Study drug administration ^r	CCI											6.1
Drug accountability					X		X	X				6.2
Return unused medication and inhaler					X		X	X				6.2
AE ^s	X	X	X	X	X	X	X	X	X	X	X	8.3
Blood samples for biochemistry	X		X ^t		X	X	X	X	X		X	8.2.4
Blood samples for haematology	X	X	X ^t		X	X	X	X	X		X	8.2.4
Blood samples for clotting profile	X											8.2.4
Blood sample for hs-CRP	X	X	X ^t		X	X	X	X	X		X	8.6.1
Blood samples for safety immuno-biomarkers	X		X ^t		X	X	X	X	X		X	8.2.5.1

Table 2 Schedule of Activities Part 2

Table 2 Schedule of Activities Part 2

Procedure	Screening	Run-in	Treatment Period ^a					ETV/ IPD	Follow-up		Unscheduled Visit	Details in CSP Section or Appendix
Visit	1	2	3	4	5	6	7		8	9		
Day	(up to 14 days before V2) ^{b,c}	-28 ± 2	1	7 ± 2	14 ± 2	21 ± 2	28 ± 2		39 ± 6	56 ± 4		
Week	-6	-4	0	1	2	3	4		5/6	8		
SARS-CoV-2 serology ^{cc}	X											5.2, 8.2.4

Abbreviations: ACQ-6 = Asthma Control Questionnaire-6; ADA = anti-drug antibody; AE = adverse event; AESI = adverse event of special interest; CCI [REDACTED] COVID-19 = Coronavirus disease-2019; CRP = C-reactive protein; CSP = clinical study protocol; ECG = electrocardiogram; e-Diary = electronic diary; ETV = early termination visit; FEV₁ = forced expiratory volume in 1 second; FeNO = fractional exhaled nitric oxide; FSH = follicle stimulating hormone; FVC = forced vital capacity; CCI [REDACTED] HBsAg = hepatitis B surface antigen; HIV = human immunodeficiency virus; CCI [REDACTED]

CC [REDACTED] HRT = hormone replacement therapy; hs-CRP = high sensitivity CRP; IgE = immunoglobulin E; IPD = Intervention Discontinuation Visit; CCI [REDACTED] PCR = polymerase chain reaction; PEF = peak expiratory flow; PK = pharmacokinetics; RNA = ribonucleic acid; QFT = QuantiFERON; SARS-CoV-2 = severe acute respiratory syndrome coronavirus 2; SPFQ = Study Participant Feedback Questionnaire; TB = tuberculosis

^a In-clinic outpatient visits during the Treatment Period will be scheduled so that they fall at the time of morning dose administration.

^b Time between Visit 1 and Visit 2 may be extended up to 28 days upon input from the Study Physician.

^c Visit 1 can be done on several/different days prior to Visit 2.

^d Height at Visit 1 only.

^e A complete physical examination including an assessment of the general appearance, respiratory, cardiovascular, abdomen, skin, head and neck (including ears, eyes, nose and throat), lymph nodes, thyroid, musculoskeletal and neurological systems will be performed.

^f A brief physical examination including an assessment of the general appearance, skin, abdomen, cardiovascular, and respiratory systems will be performed.

^g Vital signs will be measured pre-dose at the scheduled morning dosing in-clinic visits.

^h Refresher training if required.

ⁱ Check if participant has enough rescue medicine for use at-home use and refill if necessary.

^j FeNO will be measured pre-spirometry, pre-dose (as applicable), and pre-bronchodilation.

^k Spirometry will be performed 45 minutes and 15 minutes prior to first dose of study intervention on Day 1 and pre-dose at all other visits. If possible, all post-randomisation pre-dose morning clinic device spirometry assessments should be performed within ± 1.5 hours of the time that the 15 min prior to randomisation spirometry was performed.

^l Reversibility testing will be performed 15 to 30 minutes after inhalation of 400 µg of salbutamol.

^m ECG will be measured before study drug administration on Day 1 (within 75 min), and 1 hour (± 20 min) after administration of study intervention on post randomisation visits as indicated.

ⁿ SPFQ (optional) will not be completed at unscheduled visits.

^o At-home spirometry will be completed up to V8 and only to be completed at non-clinic visit timepoints.

^p At Visit 1 the e-Diary is set up, participants perform training and ACQ-6 is completed.

q The e-Diary will be completed twice daily during the Run-in, Treatment, and Follow-up Period.

r Study intervention will be administered **CCI**

28). Date and time of administration at home will be registered in the e-Diary by the participant. Study drug administration at the clinic will be under supervision. The Day 28 dosing window \pm 2 days should only be used if needed, and where possible to keep within \pm 1 day.

s AEs will be collected from the time of informed consent. Unscheduled safety sampling may be performed at the discretion of the Investigator in the event of AEs/AESIs, including but not limited nasal swabs to confirm infection.

t Baseline safety sampling will be performed pre-dose on Day 1.

u Blood samples will be analysed for IgE if potential drug related IgE response is observed in any participant.

v Local CRP may be performed from Visit 3 and throughout the study in the event of AE/AESI as required to inform suspension/stopping criteria.

w PCR may be performed to confirm hepatitis B / hepatitis C status if required. Additional evaluation may be required in participants with any signs of active TB at the time of screening or positive interferon-gamma release assay (IGRA, QuantiFERON®-TB Gold) test according to the local standard of care.

x Blood samples for PK measurements will be collected in all participants pre-dose at each visit, including unscheduled visits. Intense sampling may be performed in approximately 25% of participants per treatment arm (for example, 20 subjects in the **Q**mg treatment arm). Timing of intense samples: Day 1: 1, 2, 3 (\pm 10 min), 6, and 8 h (\pm 20 min), Day 21 4 h post-morning dose (\pm 20 min) and Day 28 (last dose), 1, 2, 3 (\pm 10 min), 6, 8 (\pm 20 min), 24 (\pm 2 h), 48 (\pm 2.5 h), and 96 h (\pm 2.5 h; single dose of AZD1402 only on last day of dosing). PK sampling timepoints may be amended based on results from Part 1a/b. An unscheduled PK sample may be collected in the case of AEs and / or unscheduled safety blood sampling.

y ADA sampling, pre-dose Day 1, Day 14, Day 21, Day 28, and at the Follow-up Visits. An unscheduled ADA sample may also be collected in the case of AEs/AESIs and/or unscheduled safety blood sampling.

z Sample collection only if consented. If for any reason the sample is not drawn at Visit 3, it may be taken at any visit until the last study visit.

aa Proposed samples and times: Serum: Pre-dose Day 1, pre-dose Week 2, Week 4 and at Follow-up. **CCI** Pre-dose Day 1, and Week 4. **CCI** Pre-dose Day 1, Day 28, and Day 39. **CCI** Pre-dose Day 1.

bb All urine pregnancy tests will be done pre-dose. In case of a positive result, a serum pregnancy test will be performed.

cc SARS-CoV-2 serology at Screening; PCR is optional and may be performed centrally or at the local laboratory as clinically indicated and as per local guidelines for the duration of the study. Ad hoc nasal and/or throat-swab specimen is to be collected for the identification of a suspected respiratory infection during any visit. This may be performed locally, or if required by central laboratory.

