This is a randomised, placebo-controlled, double-blinded, multi-centre, 2-part study to assess the efficacy and safety of inhaled AZD1402. Part 1 will be performed in a Lead-in Cohort for each dose level to evaluate the safety and pharmacokinetics (PK) in a population with asthma controlled on medium dose ICS-LABA before progressing to at-home dosing in adults with asthma who are uncontrolled on medium-to-high dose ICS-LABA in Part 2. Part 2 will be initiated following evaluation of safety and PK in Part 1a. The study intervention in both parts of the study will be administered CCI [REDACTED] using the CCI [REDACTED] DPI for a period of 4 weeks.

A Lead-in Dose Progression and Escalation Cohort approach with 3 dose levels has been selected to confirm Phase I data dose-response observations and further evaluate safety and PK in adults with asthma controlled on medium dose ICS. The Part 1a safety cohort will be completed before progressing to at-home dosing in adults with asthma uncontrolled on medium-to-high dose ICS-LABA in Part 2.

This study will be conducted in approximately 8-10 countries. The entire study period for each participant in both Parts 1 and 2, is approximately 3.5 months; a 2-week Screening Period, a 4-week Run-in Period, 4 weeks of Treatment Period, and 4 weeks of Follow-up Period.

Part 1

Part 1 of the study will be randomised, double-blind, placebo-controlled, and conducted in parallel for the 2 CCI [REDACTED] dose levels (Part 1a) followed by an unblinded safety review and escalation to the CCI [REDACTED] dose (Part 1b) dependent on the outcome of the safety review. Data evaluated in the safety review will be unblinded; however, blinding will be maintained for participants and Investigators. The total sample size for Part 1 is estimated to be 45 participants.

The target population is adults with asthma (age 18 to 75 years, inclusive) who are adequately controlled on a stable medium dose ICS-LABA and additional rescue medication as needed, Asthma Control Questionnaire-6 (ACQ-6) score ≤ 1.0 and pre-bronchodilator forced

expiratory volume in one second (FEV₁) ≥ 70%, and with no exacerbation requiring systemic treatment or hospitalisation/emergency department visit for asthma during the 12 months prior to study start.

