Part 1a will consist of 30 participants who will be randomised 1:1:1 to receive 1 of the 2 **CCI** AZD1402 DPI doses (**CCI** or **CCI** mg) or placebo in parallel. Part 1b will consist of 15 participants who will be randomised 2:1 to receive the **CCI** AZD1402 DPI dose (**CCI** mg) or placebo. Due to logistical reasons, the randomisation in Part 1 will be stratified by site in Australia and Germany.

The target population is adults with asthma (age 18 to 75 years, inclusive) who are adequately controlled on a stable medium dose ICS-LABA (and additional rescue medication as needed), ACQ-6 score ≤ 1.0 and pre-bronchodilator FEV₁ $\geq 70\%$, and with no exacerbation requiring systemic treatment or hospitalisation/emergency department visit for asthma during the 12 months prior to study start.

The primary objective in Part 1 is to determine the safety and tolerability of AZD1402 in relation to placebo at 3 different dose levels in adults with asthma controlled on medium dose

ICS-LABA with 4 weeks of dosing and will include assessments of AEs, vital signs, safety blood samples, immuno-biomarkers, ECGs, FEV₁, and FeNO. In addition to clinic spirometry assessments, participants will receive a home spirometry device to use in-clinic and at home as described in the SoAs ([Table 1](#) and [Table 2](#)). The secondary objective is to investigate the PK profile and immunogenicity of AZD1402. A full PK and ADA profile will be taken in all participants as per the SoAs ([Table 1](#) and [Table 2](#)). Part 1 is not powered for efficacy, but exploratory endpoints will include FeNO and [CCI](#) over the 4-week Treatment Period. Additionally cough and [CCI](#) The e-Diary will be used to record daily symptoms and questionnaire data.

Participants will sign informed consent prior to participating in any study specific procedures. Visit 1 may be completed over several days prior to Visit 2. If participants are eligible at Visit 1 and the FEV₁ criterion of $\geq 70\%$ predicted and ACQ-6 score of ≤ 1.0 is met, they will return for Visit 2, beginning the Run-in Period. During the Run-in Period, all participants will continue their own stable treatment regime, which will include medium dose ICS-LABA. Treatment must remain stable for the duration of the study, unless clinically indicated adjustments are required.

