4.5.4 Immunogenicity Set

The Immunogenicity set (IS) will include all participants in the SS with at least 1 post-treatment ADA result (positive or negative), with exception for any analysis of relationship of ADA with PK where will instead include all participants in the PK set.

The immunogenicity analysis set will be used for all ADA analyses.

All the immunogenicity parameters and listings will be based on the IS and presented for each treatment group.

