4.16 Immunogenicity Evaluation

Anti-drug antibodies will be summarised as categorical variables with the number and percentages with a positive result at the specific visit. Immunogenicity titre will be summarised descriptively as a continuous variable, only for ADA positive tests, with median, interquartile range, minimum, and maximum, at each analysis visit.

ADA will also be summarised based on the IS including the following:

- ADA positive at baseline and/or post-baseline (ADA prevalence).
- Treatment emergent (TE)-ADA positive (ADA incidence): defined as the sum of treatment-induced ADA positive and treatment-boosted ADA positive.
- Treatment-induced ADA positive: defined as ADA negative at baseline and post-baseline ADA positive.
- Treatment-boosted ADA positive: defined as ADA positive at baseline and boosted the pre-existing titre post-baseline (≥ 4 -fold increase).

- TE-ADA negative: defined as ADA positive but not fulfilling the definition of TE-ADA positive.
- Both baseline and post-baseline positive.
- Only baseline positive.
- ADA persistently positive: defined as either ADA negative at baseline and ADA positive at ≥ 2 post-baseline assessments, or ADA positive at last post-baseline assessment.
- ADA transiently positive: defined as ADA negative at baseline, having at least one post-baseline ADA positive assessment and not fulfilling the conditions of ADA persistently positive.
- TE-ADA positive with maximum titre $>$ median of maximum titres.

Post-baseline includes on-treatment and follow-up phases.

The median of maximum titres is calculated based on the maximum titre for each ADA positive subject within each treatment group (including both baseline and post-baseline measurements).

All immunogenicity parameters will also be reported in listing. Days from previous dose of IP will be calculated as the ADA date minus date of previous dose. Days from previous dose of IP for ADA measured during pre-treatment period will be set to missing. Listings of all subjects excluded from the ADA analysis set will also be provided. Listing will be based on SS.

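### Part 1b has more scheduled ADA samples than Part 1a, but the SAP counts ADA incidence and persistence over all samples by dose, so short-lived positives could be misread as a dose effect

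*Protocol*

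**What the plan says.** **Schedule.** Protocol 1.3, Table 1 footnote aa, repeated in SAP 5.1, Table 2, reads "ADA sampling, pre-dose Day 1, Day 14, Day 20, Day 24 (Part 1b only) and Day 28 and on Follow-up/unscheduled visits". The ADA row of the table marks Days 20 and 24 without a cohort limit, so the limit rests on the footnote alone.

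**Cohorts.** The Synopsis states: "A Lead-in Dose Progression and Escalation Cohort approach with 3 dose levels has been selected". Protocol 4.1.1 puts two doses and placebo in the first cohort ("Part 1a will consist of 30 participants who will be randomised 1:1:1") and the escalation dose and placebo in the second ("Part 1b will consist of 15 participants who will be randomised 2:1").

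**Definitions.** SAP 4.16 gives "Treatment-induced ADA positive: defined as ADA negative at baseline and post-baseline ADA positive". Persistent positivity is "ADA negative at baseline and ADA positive at ≥ 2 post-baseline assessments, or ADA positive at last post-baseline assessment". Transient means a baseline-negative participant with some later positive who is not persistent. Both the on-treatment and follow-up phases count as post-baseline. No minimum interval between positives is set, and no restriction to visits shared by the two cohorts.

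**Presentation.** SAP 4.5.4 states: "All the immunogenicity parameters and listings will be based on the IS and presented for each treatment group". SAP 4.2 summarises by Part and treatment group, and nothing separates Part 1a placebo from Part 1b placebo. SAP 4.16 also tabulates percent positive and titre at each visit.

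**The concern.** Any-positive and two-or-more-positive are counts over the samples taken, so they rise with the number of samples even when the underlying antibody response is identical. In Part 1 the number of samples is tied to dose: every participant on the escalation dose has the denser schedule, and none on the other two doses does. The 15 Part 1 placebo participants are a mixture, 10 on one schedule and 5 on the other.

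The extra sample or samples fall on treatment, close to Days 20 and 28, and so can supply the second positive that turns a transient case into a persistent one. Immunogenicity and its effects on safety form the Part 1 secondary objective. With about 10 participants per active arm, a reader will rely on the category counts. A difference that comes from the schedule could be taken for a dose effect.

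**Working it through.** **Inputs from the documents**
- Part 1b post-baseline days: 14, 20, 24, 28, 39, 56, so k = 6.
- Part 1a: 14, 20, 28, 39, 56 (k = 5) if the restriction covers Day 24 only; 14, 28, 39, 56 (k = 4) if it also covers Day 20.
- Arm sizes: 30 at 1:1:1 gives 10 + 10 + 10 placebo; 15 at 2:1 gives 10 + 5 placebo; total 45, as planned.

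The documents give no ADA rate, so there is no figure of the plan's own to reproduce.

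**Assumptions.** All participants are ADA negative at baseline, all scheduled samples are taken, Day 56 is the last assessment, and true immunogenicity is the same in every arm. Per-sample positivity is p = 20%, with within-participant correlation ρ from 0 to 0.6 (beta-binomial).

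**Formulas**
- Any positive = 1 − P(no positive).
- Persistent under the full SAP rule = 1 − P(no positive) − [(k − 1)/k] × P(exactly one positive). A single positive on the last visit counts as persistent; a single positive elsewhere does not.

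At ρ = 0 the persistent proportion is 1 − (1 − p)^k − (k − 1)p(1 − p)^(k − 1):
- k = 6: 1 − 0.2621 − 0.3277 = 41.0%
- k = 5: 1 − 0.3277 − 0.3277 = 34.5%
- k = 4: 1 − 0.4096 − 0.3072 = 28.3%

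| Measure (p = 20%) | k = 6 | k = 5 | k = 4 | 6 v 5 | 6 v 4 |
|---|---|---|---|---|---|
| Any positive, ρ = 0 | 73.8% | 67.2% | 59.0% | 6.6 | 14.7 |
| Any positive, ρ = 0.6 | 36.1% | 34.5% | 32.6% | 1.5 | 3.5 |
| Persistent, ρ = 0 | 41.0% | 34.5% | 28.3% | 6.6 | 12.7 |
| Persistent, ρ = 0.6 | 28.4% | 26.8% | 25.0% | 1.5 | 3.4 |

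Differences are in percentage points, from unrounded values. At ρ = 0.9 the persistence gaps shrink to 0.3 (6 v 5) and 0.75 (6 v 4). At p = 5% and ρ = 0, any-positive is 26.5% v 22.6% v 18.6% and persistence 7.2% v 6.3% v 5.7% for k = 6, 5 and 4.

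**In participants.** Per arm of 10, at p = 20% and ρ = 0, the 6 v 5 gap is 10 × 0.066 = 0.7 for either measure. The 6 v 4 gap is 10 × 0.147 = 1.5 for any positive and 10 × 0.127 = 1.3 for persistence.

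**Pooled placebo (k = 6 and 5, p = 20%, ρ = 0).** Expected any-positive is (10 × 67.2 + 5 × 73.8)/15 = 69.4%. The escalation dose would sit 4.4 points above it and the other doses 2.2 points below, with no true difference.

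**Second check: one episode per participant.** Assume one positive episode of D days, with onset uniform over Days 7 to 56 (49 days).
- D = 4: no two samples fall in one episode, so the detected share is 4k/49: 24/49 = 49.0% in Part 1b, against 20/49 = 40.8% (k = 5) or 16/49 = 32.7% (k = 4).
- D = 10, called persistent. The Day 56 limb contributes 10 onset days in every schedule. Pairs of positives add 14 onset days with k = 6, 6 with k = 5 and none with k = 4. This gives 24/49 = 49.0%, 16/49 = 32.7% and 10/49 = 20.4%.
- D of 28 or more: no difference in either measure.

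**The case against.** The strongest reply is that little rests on this. Part 1 tests no hypothesis, its size has no calculation behind it, and Protocol 9.4.1 plans no formal comparison between doses. The by-visit table already allows a like-for-like comparison on shared days. Positives must pass a confirmatory assay, so treating samples as independent is an extreme case; with high correlation the gap almost vanishes. The last-sample limb of the persistence rule, "ADA positive at last post-baseline assessment", rests on a Day 56 visit common to both cohorts, which dampens the effect. All of this stands and limits the size. It does not remove the problem, because a by-visit table cannot give participant-level incidence or persistence.

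The reply also has force against replacing the main categories with a common-visit filter. A participant confirmed positive only on Day 24 would then drop out of the incidence count. It would also be unclear which ADA status drives the PK summaries (SAP 4.15.1), the AE tables (4.17.1) and the hsCRP table (4.17.2).

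Some stronger readings that a reader might infer are not supported:
- That the escalation dose alone is inflated. Its Part 1b placebo group shares the schedule.
- That comparing immunogenicity between doses is itself the secondary objective. The objective is worded for the product, with no reference to dose.
- That positives four days apart are impossible in Part 1a. Unscheduled samples are allowed in both cohorts, and on the 5-sample reading Part 1a already has scheduled samples six days apart (Days 14 and 20).

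**Conclusion.** The point holds, at modest size. As written, the Part 1 participant-level ADA categories confound sampling density with the escalation cohort, and for sporadic or short-lived positives the expected bias is towards higher counts in Part 1b. Under the assumed 20% positivity and correlation 0 to 0.6, the gap in persistence is about 2 to 7 points (6 v 5) or 3 to 13 points (6 v 4), and in any-positive about 2 to 7 or 3.5 to 15 points. That is less than one participant in an arm of 10 for one extra sample, and up to about 1.5 for two.

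These figures depend on assumed rates, correlations and episode lengths; the documents supply none. A reader might conclude that the escalation dose will look more immunogenic whatever the data. That does not follow: if ADA, once present, lasts for weeks, the schedules give nearly the same answer. Part 2 uses one ADA schedule for all arms, so the issue is confined to Part 1.

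Whether Part 1a has 5 or 4 samples cannot be settled from the text. The neighbouring PK footnote marks a Day 20 post-dose sample as Part 1b only, which makes the wider reading plausible without proving it.

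**What to change.** 1. In footnote aa, or in SAP 4.16, state whether the Part 1b restriction covers Day 20 as well as Day 24.
2. Keep the all-sample categories for the main ADA table and for the ADA-status splits of PK, AEs and hsCRP, so that no confirmed positive is discarded and the tables agree with each other.
3. Add to SAP 4.16 a companion Part 1 table of incidence, persistent and transient categories, derived only from scheduled visits common to Parts 1a and 1b: Days 14, 20, 28, 39 and 56, or the same without Day 20.
4. State that any between-dose, or dose-versus-pooled-placebo, ADA statement for Part 1 rests on that companion table.

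With common visits, k is the same in every Part 1 arm, so the difference due to the schedule is zero by construction. Missed samples can still differ by chance. The cost is one extra table and a visit filter; no new data are needed.
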